#### Efficacy:

- Baseline for WOMAC Pain score, WOMAC Function Score, and Patient response to OA question will be the most recent assessment prior to first dose
- 30% improvement in WOMAC Pain Score (yes/no) is defined as a reduction of
   ≥ 30% in the WOMAC Pain Score where reduction is defined as the relative change
   from the baseline value.

CONFIDENTIAL Page 13 of 27

Final 2.0, 11 Oct 2021

Protocol No.: XT-150-2-0204 Sponsor: Xalud Therapeutics, Inc.

For adverse events, with unknown intensity (severity) or unknown relationship to study treatment, these will be imputed as follows:

- If the intensity (severity) of an adverse event is unknown/missing, the intensity will be imputed for the summary of adverse events as being "Grade 3: Severe".
- If the relationship to investigational product of an adverse event is unknown/missing, the relationship will be imputed for the summary of adverse events as being the least favourable relationship, i.e., "Related".

For adverse events, where either the onset time or resolution time is unknown, time since first dose and duration will be imputed as follows:

- If onset date is unknown, and it cannot be confirmed that onset was prior to the start
  of dose administration, then the AE will be classified as treatment-emergent, with
  unknown time since first dose.
- If either the date of onset or the date of resolution is unknown, then duration will be shown as unknown.

For WOMAC, the scores will be imputed as follows:

- WOMAC Pain score will be calculated as the average of the corresponding non-missing sub items, multiplied by 5. In cases where 2 or more questions are missing, the WOMAC Pain score will not be imputed and will be set to missing
- WOMAC Function score will be calculated as the average of the corresponding non-missing sub scores, multiplied by 17. In cases where 4 or more questions are missing, the WOMAC Pain score will not be imputed and will be set to missing

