10.4 Adverse Event Reporting

The Sponsor has obligations for expedited reporting of SAEs meeting specific criteria to worldwide regulatory authorities. Therefore, the Sponsor must be notified immediately regarding any SAE that occurs after informed consent.

All SAEs must be reported to the Medical Monitor by phone or email within 24 hours of the investigational site's knowledge of the event.

All SAEs and discontinuations due to AEs will be reported to the IRB/HREC.

The study site will also transmit a Serious Adverse Event Report (SAER) to the site study monitor and sponsor by facsimile or email within 24 hours. Contact details will be provided to all sites. An optional initial report can be made via telephone, but a completed SAER must still be faxed or emailed within 24 hours of the site's knowledge of the event. The study sites will be provided with SAER forms wherein the following information is requested.

- Participant identification, Investigator name, and site number
- SAE information: event term, onset date, severity, and causal relationship

- The outcomes attributable to the event (i.e., death, a life-threatening AE, inpatient hospitalization, prolongation of existing hospitalization, a persistent or significant disability or incapacity, or other important medical event[s])
- A summary of relevant test results, pertinent laboratory data, and any other relevant medical history
- The first and last dates of study drug administration. NOTE: as this is a double-blind study, SAERs should not indicate specific study drug assignments
- Indicate if the study drug was discontinued or the study drug administration schedule modified
- Supplemental information may include the following hospital records: laboratory results, radiology reports, progress notes, admission and emergency room notes, holding and observation notes, discharge summaries, autopsy reports, and death certificates

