10.6.2 Severity

All AEs will be graded for severity to describe the maximum intensity of the AE based on Common Terminology Criteria for Adverse Events (CTCAE) criteria (version 5.0). For purposes of consistency, these intensity grades are defined in Table 6.

Table 6. Guidelines for Severity Assessments

Grade 1	Mild; asymptomatic or mild symptoms; clinical or diagnostic observations only; intervention not indicated
Grade 2	Moderate; minimal, local or non-invasive intervention indicated; limiting age-appropriate instrumental activities of daily living (e.g., preparing meals, shopping for groceries or clothes, using the telephone, managing money)
Grade 3	Severe or medically significant but not immediately life-threatening; hospitalization or prolongation of hospitalization indicated; disabling; limiting self-care activities of daily living (bathing, dressing and undressing, feeding self, using the toilet, taking medications, and not bedridden)
Grade 4	Life-threatening consequences; urgent intervention indicated
Grade 5	Death related to adverse event

These criteria, in addition to good clinical judgment, should be used as a guide for determining the causal assessment. If the event is believed to be unrelated to study drug administration, then an alternative explanation should be provided.

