#### 5.5. Data Derived by Calculation

The following data fields for inclusion in the data listings will be derived by calculation as per the Clinical Data Interchange Standards Consortium (CDISC) standard:

Adverse Events:

• Treatment for adverse event, assigned as

```
Non-Treatment-Emergent if (Onset Date) < (Date of Stage A Dose)
```

[figure not shown]
Treatment for Stage A if
(Onset Date) >= (Date of Stage A Dose) &
(Onset Date) < (Date of Stage B Dose);

Treatment for Stage B if (Onset Date) >= (Date of Stage B Dose)

CONFIDENTIAL Page 12 of 27

Protocol No.: XT-150-2-0204 Sponsor: Xalud Therapeutics, Inc.

- Adverse event time since Stage B dose (in days), calculated as
   (Onset Date) (Date of Stage B Dose) if (Onset Date) >= (Date of Stage B
   Dose)
- Adverse event time since Stage B dose is Not Applicable if if (Onset Date) < (Date of Stage B Dose)

- Adverse event duration (in days), calculated as (Resolution Date

  – Onset Date)

Safety Assessments Change from Baseline:

Baseline for vital signs and clinical laboratory parameters will be the most recent
assessment prior to first dose [which may be an unscheduled assessment, a repeat of
a scheduled Baseline assessment, or the screening assessment if separate Baseline
assessments are not performed]

Clinical Safety Laboratory Assessments:

- If a clinical laboratory result is above the upper limit of normal, then Out of Range flag will be set to "H"
- If a clinical laboratory result is below the lower limit of normal, then Out of Range flag will be set to "L"
- Clinical Laboratory parameters that are outside the reference range and medically assessed as clinically significant will be identified as "Abnormal CS"
- Clinical Laboratory parameters that are outside the reference range and not medically assessed as clinically significant will be identified as "Abnormal NCS"

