#### 8.2. Safety Data Presentation and Analysis

All clinical safety and tolerability data will be listed for each subject.

Safety data will be summarized using descriptive statistics. Where summaries include changes from baseline, the relevant baseline value will be determined as described in Section 5.5 above.

All adverse events will be listed using MedDRA terms, as coded per the Data Management Plan. The number and percentage of subjects with at least one treatment emergent AE and the number of treatment emergent AEs reported will be summarized by dose level or treatment, grouped according to system organ class and preferred term, using descriptive statistics. The order for system organ class will be according to the Internationally Agreed Order, as per the guidance document MedDRA® *Data Retrieval and Presentation: Points to Consider*, specific to the MedDRA version used for this study. Summaries of TEAEs will also be presented by severity (graded according to the NCI CTCAE version 5.0) and by relationship to investigational product. In these summaries, subjects will be counted at most once per MedDRA term, for the AE of highest severity or least favorable relationship. Summaries will also be presented for SAEs and for AEs leading to study withdrawal.

Clinical laboratory parameters for hematology, serum chemistry, and coagulation will be listed. Summaries of reported results, including changes from baseline and medical

CONFIDENTIAL Page 16 of 27

Protocol No.: XT-150-2-0204 Sponsor: Xalud Therapeutics, Inc.

assessments, will be presented by treatment group and study timepoint. Individual subject profiles will be presented for any laboratory parameters with at least one post-dose value outside the laboratory's reference ranges and deemed clinically significant.

Vital signs will be listed and summarized by dose level / treatment and study timepoint. A summary of changes from pre-dose baseline will also be presented.

Changes in physical examination findings over time will be listed by body system for each subject. It is noted that any untoward findings identified on physical examinations after the administration of the first dose of study medication will be captured as an adverse event if those findings meet the definition of an adverse event as defined in the protocol.

Injection site examinations will be listed and summarized by dose level / treatment and study timepoint.

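### An adverse event with no recorded grade is tabulated as Grade 3 even when its outcome is known to be fatal or life-threatening, and an undated event after two injections has no assigned treatment

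*SAP*

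**What the plan says.** The SAP's table of contents lists 5.6 Handling of Missing Data. Its heading is not visible in the public text, but its adverse-event rules follow the efficacy derivations at the end of 5.5. Three of them matter here.

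- **Missing severity:** "the intensity will be imputed for the summary of adverse events as being 'Grade 3: Severe". No exception is stated.
- **Missing relationship:** "the relationship will be imputed for the summary of adverse events as being the least favourable relationship", that is, related.
- **Unknown onset:** if onset before dosing cannot be confirmed, "then the AE will be classified as treatment-emergent", with time since first dose left unknown. No stage or treatment is named.

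The scale is in Protocol 10.6.2, Table 6, which has five CTCAE grades. Grade 4 reads "Life-threatening consequences; urgent intervention indicated" and Grade 5 reads "Death related to adverse event". SAP 8.2 uses it: "Summaries of TEAEs will also be presented by severity (graded according to the NCI CTCAE version 5.0"). In that table a participant is counted at most once per MedDRA term, at the highest severity.

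SAP 5.5 assigns an event to a treatment by comparing its onset date with the two dose dates. The Stage A line, for example, begins with the condition "Onset Date) >= (Date of Stage A Dose". SAP 8.2 summarizes treatment-emergent events by dose level or treatment.

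**The concern.** Grade 3 is the top of a mild, moderate, severe scale, but it is the middle of the scale this trial uses. As a default it is cautious for an ungraded event that was mild or moderate. It is the reverse for an ungraded event that was life-threatening or fatal, and there the plan would replace something already known with a lower value. The neighbouring rule for relationship goes to the worst category, so the section as a whole aims at caution and misses it in this one case.

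The onset rule has a gap of a different kind. It settles whether an undated event counts as treatment-emergent, but not under which treatment. In a design where a participant may move from placebo to XT-150, or from one dose to another, that choice can decide which column carries the event.

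Safety and tolerability are the primary objective, and the rows for Grades 4 and 5 are likely to be the sparsest in the table.

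**Working it through.** No sample-size, power or error-rate figure is involved. The check applies each written rule to each possible case.

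**Severity rule.** Inputs: the five grades in Protocol 10.6.2, Table 6, and the imputed value 3 from SAP 5.6. Shift = 3 − true grade.

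| True grade, not recorded | Tabulated as | Shift |
|---|---|---|
| 1 | 3 | +2 |
| 2 | 3 | +1 |
| 3 | 3 | 0 |
| 4 (life-threatening) | 3 | −1 |
| 5 (death) | 3 | −2 |

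The rule raises or preserves severity for Grades 1 to 3 and lowers it only for Grades 4 and 5.

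**Can the grade be missing while the outcome is known?** Protocol 10.4 says the report form requests severity and also "The outcomes attributable to the event (i.e., death, a life-threatening AE, inpatient hospitalization" and the remaining seriousness outcomes. The same section sets a shorter minimum for a valid report: the participant, the reporting source, and an event or outcome. Severity is not in that minimum, so a report with a fatal outcome and no grade is possible. The list of CRF items in Protocol 10.3 includes severity but not outcome, so the outcome has to be read from the serious adverse event report.

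**Onset rule.** SAP 5.5 has three lines: onset before the Stage A dose (not treatment-emergent); onset on or after the Stage A dose and before the Stage B dose (Stage A treatment); onset on or after the Stage B dose (Stage B treatment). Test cases with doses on Day 0 and Day 200:

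- Onset on Day 100 meets only the second line: Stage A.
- Onset on Day 250 meets only the third line: Stage B.
- With onset unknown, none of the three comparisons can be evaluated, so no line is met. SAP 5.6 still calls the event treatment-emergent unless pre-dose onset is confirmed.

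**Where the missing assignment is a real ambiguity.** A participant with one injection has only one possible treatment. With two injections, the treatment differs between stages in four of the six sequences in SAP 4.4 (150 then 450, 450 then 150, placebo then 150, placebo then 450). At about 45 per sequence this is 4 × 45 = 180 of 270 participants, of whom 2 × 45 = 90 go from placebo to XT-150. These are ceilings, because the second injection is optional. They count participants who could be affected, not undated events.

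**The case against.** The strongest reply is that the severity case is hard to reach and does little damage. Protocol 10.3 requires onset date, severity and relationship for every event. Protocol 10.4 requests them again on the serious event report. Protocol 14.2 has the investigator sign the CRF only after queries are resolved. It can also be argued that the intensity of an event known to be fatal is not unknown, since Table 6 defines Grade 5 by death. And imputing the worst grade to every ungraded event would be absurd, so Grade 3 is a reasonable general default.

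Most of this stands, and it limits the point to a minor one. It does not remove it: the rule as written turns on a missing intensity, has no exception, and does not tell the programmer to look at the outcome first.

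A reader might infer that deaths or life-threatening events would vanish from the safety results. The documents do not support that. SAP 8.2 plans a separate summary of serious adverse events that does not depend on grade, and all safety data are listed by subject. The distortion is confined to the by-severity table.

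A reader might also infer that undated events would drop out of the by-treatment tables. That is not shown either. SAP 5.5 describes its derived fields as being for the data listings and does not say that the summaries use them. A figure is also missing inside the assignment rule in the public copy. What can be said is that no visible rule assigns the event.

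**Conclusion.** The point holds as a minor correction to the safety tabulation. SAP 5.6 would place an ungraded event with a recorded life-threatening outcome one grade too low, and one with a recorded fatal outcome two grades too low, in the by-severity table of treatment-emergent events. The event would still be visible among the serious adverse events.

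The documents give no expected number of deaths, of missing grades or of undated events, so no count can be given beyond saying that cases should be rare. Any suggestion that a material share of the safety results is affected would be unsupported.

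The onset gap is secondary. It matters only for an event whose onset is unknown, which cannot be confirmed as pre-dose, in a participant with two injections, and chiefly where the two treatments differ.

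Both conclusions assume that the visible adverse-event rules in 5.5 and 5.6 are complete.

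**What to change.** **Severity (SAP 5.6).** Before imputing a missing grade, set Grade 5 if the serious adverse event report records death as the outcome of that event, and Grade 4 if it records the life-threatening criterion. Otherwise keep Grade 3 as now. Footnote the number of grades derived or imputed, by treatment.

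**Unknown onset (SAP 5.5 or 5.6).** Where pre-dose onset cannot be confirmed, bound the onset by the visit at which the event was first recorded and the visit before it. Protocol 9.5 to 9.7 collect events since the last visit, so the interval is available. Assign the treatment in force over that interval; with one injection this is the only treatment received. If the second injection falls inside the interval, apply one pre-specified rule: for example, the active treatment if the other is placebo, and the higher dose if both are active. Always choosing the second injection would not be cautious for the 450-then-150 sequence, because it would move the event to the lower dose. Footnote the number of events placed in this way.

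The cost is two sentences in the SAP and minor programming. It assumes that the outcome on the serious adverse event report can be linked to the event record. No sample size, power or error rate changes.

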13.5.1 Multiplicity of endpoints

The statistical analysis of the primary endpoint will preserve a familywise error rate of 0.025 (one-sided), accounting for statistical tests of each of the two XT-150 doses to placebo with respect to the primary endpoint.

[figure not shown]
P-values from analyses of other endpoints may be interpreted as descriptive statistics.

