13.5.2 Statistical methods for the binary outcomes

Whether the subject achieves at least a 30% improvement from baseline in WOMAC Pain Score at Day 180 will be coded as a binary outcome: responder or non-responder. Subjects who withdraw from study before Day 180 or otherwise do not provide a response at that time point will be considered non-responders. The response outcome will be analyzed in a logistic regression model with treatment as the main factor and baseline WOMAC pain as a covariate. Within this model, z-tests will be used to compare the two XT-150 doses to placebo, with step-down Dunnett-like adjustments for multiplicity of doses. Handling of special cases, such as zero responders in a treatment group, will be addressed in the SAP.

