13.5.3 Statistical methods for the continuous or graded endpoints

Continuous or graded responses, including changes from baseline in WOMAC Function and patient response, as well as KOOS and BPI items, will be analyzed in a repeated-measures analysis of covariance model with treatment, Study Day and their interactions as the main factors and the baseline value of the endpoint as a covariate. Missing data will not be imputed before such analyses. Within this model, t-tests will be used to compare the two XT-150 doses to placebo, with step-down Dunnett-like adjustments for multiplicity of doses. Within such models, changes from baseline may be analyzed at other time points (Days 7 [±1 day], 30 [±2 days], 60 (±7 days), 90 [±7 days], 120 [±7 days], and 150 [±7 days]). Additional efficacy analyses may be performed using alternate models.

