#### 9.3. Efficacy Analysis

All inferential analyses of efficacy will be based on the first 180 days after dose administration (Stage A) and on the analysis of time from Day 0 until patient request for a second injection.

CONFIDENTIAL Page 18 of 27

Final 2.0, 11 Oct 2021

Sponsor: Xalud Therapeutics, Inc.

Protocol No.: XT-150-2-0204

[figure not shown]
For the statistical analysis of the primary efficacy endpoint, a logistic regression (response: 30% improvement at Day 180 (yes/no)) will be performed to compare 150 µg XT-150 with placebo and 450 µg XT-150 with placebo statistically. The model will include a fixed effect for treatment and the subject's baseline WOMAC pain score as a covariate. From this model, the 150 µg XT-150 to placebo and 450 µg XT-150 to placebo odds ratio of reduction and its two-sided 95% CI will be calculated. In this analysis, a subject who does not provide a response at Day 180 will be considered a non-responder (i.e., improvement will be set to "no").

In the event that one or more treatment arms has no responders, which would cause numerical difficulties in the logistic regression model, the statistical analysis will add 2 successes and 2 failures to each treatment group. This based on the recommendation in Agresti and Caffo, "Simple and Effective Confidence Intervals for Proportions and Differences of Proportions Result from Adding Two Successes and Two Failures," The American Statistician, Vol. 54, No. 4 (Nov., 2000), pp. 280-288.

The change from baseline in WOMAC Function Score will be analyzed using a repeated measures model including fixed effects for treatment (i.e., 150 µg XT-150, 450 µg XT-150, placebo), study day (i.e., Day 7, 30, 60, 90, 120, 150, 180) and treatment by study day interaction. In addition, the subject's baseline score will be included as a covariate. From the model, the treatment differences between 150 µg XT-150 and placebo, and 450 μg XT-150 and placebo will be estimated for the average effect of the first 180 days after dose administration (i.e., Stage A). Additionally, p-values and corresponding two-sided 95% confidence intervals will be provided.

The change from baseline in WOMAC Pain Score will be analyzed similarly.

Change from baseline in total and individual BPI, change from baseline in KOOS, and change from baseline in the patient response will be analyzed similarly.

CONFIDENTIAL Page 19 of 27

Final 2.0, 11 Oct 2021

Protocol No.: XT-150-2-0204 Sponsor: Xalud Therapeutics, Inc.

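### The WOMAC Function scoring bullet sets the Pain score to missing, so as written Function has no missing-item limit and a complete Day 180 Pain score can be voided

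*SAP*

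**What the plan says.** SAP section 5.6 (Handling of Missing Data) has two WOMAC scoring bullets, both complete.

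- **Pain.** The score is the mean of the answered items times 5. Its limit is: "In cases where 2 or more questions are missing, the WOMAC Pain score will not be imputed and will be set to missing".
- **Function.** "WOMAC Function score will be calculated as the average of the corresponding non-missing sub scores, multiplied by 17". Its limit is: "In cases where 4 or more questions are missing, the WOMAC Pain score will not be imputed and will be set to missing".

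The second limit therefore acts on Pain, although it stands in the Function bullet. No other visible text gives a missing-item limit for Function. The SAP Addendum uses both scores again at Day 180 and Day 360 and does not restate the rule.

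A missing Pain score has these consequences:

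- **Primary endpoint.** SAP 9.3 says that "a subject who does not provide a response at Day 180 will be considered a non-responder". Protocol 13.5.2 is to the same effect: "Subjects who withdraw from study before Day 180 or otherwise do not provide a response at that time point will be considered non-responders".
- **Change in Pain.** After describing the repeated-measures model for Function, SAP 9.3 adds: "The change from baseline in WOMAC Pain Score will be analyzed similarly". For such models Protocol 13.5.3 says: "Missing data will not be imputed before such analyses".

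**The concern.** The Function bullet should limit how incomplete a Function score may be. As written it puts a second limit on Pain instead. Two things follow.

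1. Function, a secondary endpoint, can be pro-rated from any number of answered items.
2. Blanks in the Function section may void a Pain score whose own items are all present. That would turn an observed Day 180 responder into a non-responder and remove a valid value from the analysis of change in Pain.

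The sentence governs how analysis variables are derived, so a programmer could implement it as it stands. The SAP Addendum records that the database was already locked and unblinded when it was written. If the choice between readings is still open or undocumented, it would now be made with treatment known.

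**Working it through.** **Inputs.** From the documents: Pain is the mean times 5 and Function the mean times 17 (SAP 5.6). Pain runs from 0 to 20, so items are scored 0 to 4 and Function runs from 0 to 17 × 4 = 68. There are 90 participants per arm, with planned response rates of 30% and 10% (Protocol 13.1, SAP 4.5) and one-sided familywise alpha of 0.025 (Protocol 13.5.1). Assumed, because the documents give no figure: the share of participants affected, the item SD and the inter-item correlation.

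**Step 1: the possible readings.**

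| Reading of the Function bullet | Function limit | Complete Pain score voided? |
|---|---|---|
| Literal; questions = 17 Function items | none | yes, at 4 or more Function blanks |
| Literal; questions = 5 Pain items | none | no; redundant, since 2 or more already voids Pain |
| Corrected to Function | missing at 4 or more; at least 14 answered needed | no |

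Function has no limit under either literal reading. The voiding of Pain arises only under the first.

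**Step 2: one participant under the first reading.** Baseline Pain is 12 and Day 180 Pain is 6, with all 5 Pain items answered. The reduction is (12 − 6)/12 = 50%, above the 30% threshold, so this is a responder. With 4 of 17 Function items blank, Pain is set to missing and the participant would most naturally be coded a non-responder.

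**Step 3: the plan's power figure.** The plan gives 95% for at least one dose and 85% for both at 30% versus 10%. The method behind its table is not stated.

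- A Wald test on the log odds ratio without the baseline covariate, with Dunnett critical value 2.212 (correlation 0.5) and step-down second value 1.960, gives 96.2% and 87.5%.
- A pooled z-test with continuity correction and step-down gives 94.8% and 83.5%.

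The plan's figures lie between these. The Wald version is used below, by exact binomial enumeration with 0.5 added to cells when one is zero. It starts somewhat above the plan's table, so read the changes rather than the levels.

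**Step 4: effect on the primary endpoint.** One voided responder costs 1/90 = 1.1 percentage points. If a share L is voided equally in every arm, the rates become 0.30(1 − L) and 0.10(1 − L), and the difference is 20(1 − L) points. L of 1% to 5% is 0.9 to 4.5 participants per arm.

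| L | Difference (points) | At least one dose | Both, single-step Dunnett (SAP section 10) | Both, step-down (Protocol) |
|---|---|---|---|---|
| 0 | 20.0 | 96.2% | 80.4% | 87.5% |
| 1% | 19.8 | 96.0% | 79.8% | 87.0% |
| 2% | 19.6 | 95.7% | 79.1% | 86.5% |
| 5% | 19.0 | 95.0% | 76.9% | 84.8% |

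**Step 5: effect on Function.** With k items answered, item SD 1, inter-item correlation r and items missing at random, the SD of the pro-rating error is 17 × √[(1 − r)(1/k − 1/17)].

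- k = 14, the fewest allowed under the evident rule: 1/14 − 1/17 = 0.0126, giving 1.3 points (r = 0.5) or 1.0 (r = 0.7) on the 68-point scale.
- k = 4: 1/4 − 1/17 = 0.1912, giving 5.3 or 4.1 points.
- k = 1: the score can only be 0, 17, 34, 51 or 68.

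The k = 4 case has a plausible route. In the KOOS form (Protocol Appendix 3) the instruction text repeats before A3 and before A16, which suggests page breaks. Skipping A3 to A15 leaves A1, A2, A16 and A17, with the pain section complete. The documents do not say how often this happens.

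**The case against.** The best case against is that the intention is not in doubt. The sentence sits in the Function bullet beside the multiplier 17, and a limit of 4 Pain items would do nothing after a limit of 2. The Pain bullet is correct and complete in itself. Losing a complete Pain score needs four things together: the score name is programmed literally, the questions are read as Function items, someone completes Pain but leaves at least 4 Function items blank at Day 180, and a score voided by derivation counts as no response. The KOOS form also tells participants to answer every question. The rates behind the power figures are assumed, and even at 5% the loss for at least one dose is 1.2 points, the same size as the gap between the recomputed 96.2% and the plan's 95%. The Function consequence touches only results of which Protocol 13.5.1 says "P-values from analyses of other endpoints may be interpreted as descriptive statistics".

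Most of this stands and limits the weight of the point. The Pain consequence is conditional, and the documents do not say that a score voided by derivation is a failure to provide a response. But an obvious intention does not show which rule was programmed, and no literal reading gives Function a limit.

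**Conclusion.** The rule is wrong as written, and the effect is probably small. The missing Function limit follows from any literal reading. The loss of a complete Pain score follows from the natural reading of the questions in that bullet, and non-responder coding is then its most natural result. The size on the primary endpoint rests on an assumed 1% to 5% of participants affected equally across arms. At that level the expected difference falls by 0.2 to 1.0 point, power for at least one dose by 0.2 to 1.2 points, and power for both doses under the SAP's single-step test by 0.6 to 3.5 points. Pro-rating error in Function could be about four times as large with 4 items answered as with 14 (5.3/1.3 or 4.1/1.0), under the assumed item SD and correlations.

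**What to change.** Issue a SAP erratum to section 5.6 that replaces Pain with Function in the last sentence of the Function bullet and specifies that the count is of the 17 Function items. The threshold of 4 stays as the sponsor set it. Add that the Pain score depends only on its own 5 items.

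Because the database is reported as locked and unblinded, also document which rule the derivation program used and how many participants and visits it affected. If the literal rule was used, rerun the Pain responder, Pain change and Function outputs, including those in the Addendum.

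The cost is a one-word correction, a clarifying line and a check of the derivation program. A rerun is conditional on what that check finds.
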